# 1 PROTOCOL SYNOPSIS

Trial Sponsor	Alcon Research, LLC [name]
Name of Test Product(s)	LID017569
Name of Control Product(s)	CooperVision® Biofinity® contact lenses (Biofinity)
Title of Trial	Clinical Performance Assessment of a Daily Wear Monthly Replacement Soft Silicone Hydrogel Contact Lens
Protocol Number	CLY935-C007
Number of Sites	~3
Country	US
Planned Duration of Exposure	~ 60 days total duration (test and control) Test Product: ~30 days Control Product: ~30 days
Number of Subjects	Target to complete: 32 Planned to enroll: ~36
Study Population	Volunteer subjects aged 18 or over who are habitual spherical weekly/monthly soft contact lens wearers (excluding Biofinity wearers), have at least 3 months of contact lens wearing experience, and who wear their habitual lenses at least 5 days per week and at least 8 hours per day.
Objective(s)	The primary objective of this study is to describe the clinical performance of an investigational silicone hydrogel contact lens over 30 days of daily wear.
Endpoints	
Primary Effectiveness
 
 
Distance VA (logMAR) with study lenses
 
 

	

• [Redacted]

■ [Redacted]

■ [Redacted]

■ [Redacted]

■ [Redacted]

■ [Redacted]

 
Safety
 

• Adverse Events (AEs)

• Biomicroscopy findings

• Device deficiencies

Assessments	
Effectiveness
 

• Distance VA (logMAR) with study lenses

• Distance VA (logMAR) habitual correction

• Manifest refraction

• BCVA (logMAR distance with manifest refraction)

• [Redacted]

[Redacted]

■ [Redacted]

[Redacted]

■ [Redacted]

[Redacted]

■ [Redacted]

[Redacted]

■ [Redacted]

[Redacted]

[Redacted]

[Redacted]

• [Redacted]

■ [Redacted]

■ [Redacted]

 
Safety
 

• AEs

• Biomicroscopy

• Device deficiencies

Study Design	 Prospective  Single group  Parallel group  Crossover  Other	 Single-masked (trial subject)  Single-masked (Investigator)  Double-masked  Open-label  Other
	 Contralateral  Bilateral  Monocular lens wear	 Randomized
	Randomization scheme: Sequence 1: LID017569 → Biofinity Sequence 2: Biofinity → LID017569	
Test Product Details	Primary component/material	[REDACTED]
	LID Number	LID017569
	Manufacturer	Alcon
	Other	-1.00 to -6.00 D, 0.25 D steps
Control Product Details	Primary component/material	comfilcon A
	Product Name	Biofinity
	Manufacturer	CooperVision
	Other	-1.00 to -6.00 D, 0.25 D steps
Inclusion Criteria	
 
1. Subject must be at least 18 years of age.
 
2. Subject must be able to understand and must sign an ICF that has been approved by an IRB.
 
3. Successful wear of spherical weekly/monthly soft contact lenses in both eyes for a minimum of 5 days per week and 8 hours per day during the past 3 months.
 
4. Manifest cylinder <math>\leq 0.75</math> D in each eye.
 
5. BCVA better than or equal to 0.0 logMAR in each eye.
 
6. Subject must possess spectacles that provide a corrected VA of 20/40 or better OU, as needed.
 
7. Subject must be willing to stop wearing their habitual contact lenses for the duration of study participation.
 
8. Able to wear contact lenses within a range of sphere power from -1.00 to -6.00 D (0.25 D steps) and subject
 
	

	
willing and able to wear the study lenses for the full duration of the study.


Exclusion Criteria
	
 
1. Any anterior segment infection, inflammation, or abnormality or disease (including systemic) that contraindicates contact lens wear, as determined by the Investigator.
 
2. Any use of systemic or ocular medications for which contact lens wear could be contraindicated, as determined by the Investigator.
 
3. History of refractive surgery or plan to have refractive surgery during the study or irregular cornea in either eye.
 
4. Ocular or intraocular surgery (excluding placement of punctal plugs) within the previous 12 months or planned during the study.
 
5. Biomicroscopy findings at screening that are moderate (Grade 3) or higher and/or corneal vascularization that is mild (Grade 2) or higher; presence of corneal infiltrates.
 
6. Current or history of pathologically dry eye in either eye that, in the opinion of the Investigator, would preclude contact lens wear.
 
7. Current or history of herpetic keratitis in either eye.
 
8. Eye injury in either eye within 12 weeks immediately prior to enrollment for this trial.
 
9. Current or history of intolerance, hypersensitivity or allergy to any component of the study products.
 
10. Wearing habitual contact lenses in an extended wear modality (routinely sleeping in lenses for at least 1 night per week) over the last 3 months prior to enrollment.
 
11. Any use of topical ocular medications, artificial tear or rewetting drops that would require instillation during contact lens wear.
 
12. The Investigator, his/her staff, family members of the Investigator, family members of the Investigator’s staff, or individuals living in the households of the aforementioned persons may not participate in the study.
 
13. Participation of the subject in a clinical trial within the previous 7 days or currently enrolled in any clinical trial.
 

	14. Habitual Biofinity contact lens wearers. 15. Monovision contact lens wearers.
Associated Materials	

• OPTI-FREE® RepleniSH® multi-purpose disinfection solution (RepleniSH)

• Lubrication/rewetting drops will not be permitted during lens wear. However, habitual lubrication/rewetting drop usage is allowed up to 10 minutes prior to lens insertion and any time after lens removal. No lubrication/rewetting drop use will be allowed during clinic visits.

**Table 1-1 Schedule of Study Procedures and Assessments**

Procedure/ Assessment	Visit 1 Screen / Baseline/ Lens 1: Dispense [Day 1]	Visit 2 Lens 1: Week 1 Follow-up [Day 8 (± 2 days)] §	Visit 3 Lens 1: Month 1 Follow-up [Day 30 (± 2 days)] Lens 2: Dispense [Day 1]		Visit 4 Lens 2: Week 1 Follow-up [Day 8 (± 2 days)] §	Visit 5 Lens 2: Month 1 Follow-up/ Exit^ [Day 30 (± 2 days)] §	Unscheduled Visit
			Follow-up Lens 1 §	Dispense Lens 2			
Informed Consent	X						
Demographics	X						
Medical History	X	X	X	X	X	X	X
Concomitant Medications	X	X	X	X	X	X	X
Inclusion/ Exclusion	X						
Habitual lens (brand, power*, care)	X						
VA w/ habitual correction* (OD, OS, logMAR distance)	X					X	(X)
████████████████████	█		█			█	
Manifest refraction*	X	(X)	(X)	(X)	(X)	(X)	(X)
BCVA* (OD, OS, logMAR distance with manifest refraction)	X	(X)	(X)	(X)	(X)	(X)	(X)
Biomicroscopy	X	X	X		X	X	X
████████████████████	█	█	█	█	█	█	█
Randomization	X						
Dispense study lenses	X			X			(X)
VA w/ study lenses, (OD, OS, logMAR distance)	X	X	X	X	X	X	(X)
████████████████████	█	█	█	█	█	█	█
████████████████████	█	█	█	█	█	█	█

Printed By:

Print Date:

Procedure/ Assessment	Visit 1 Screen / Baseline/ Lens 1: Dispense [Day 1]	Visit 2 Lens 1: Week 1 Follow-up [Day 8 (± 2 days)] §	Visit 3 Lens 1: Month 1 Follow-up [Day 30 (± 2 days)] Lens 2: Dispense [Day 1]		Visit 4 Lens 2: Week 1 Follow-up [Day 8 (± 2 days)] §	Visit 5 Lens 2: Month 1 Follow-up/ Exit^ [Day 30 (± 2 days)] §	Unscheduled Visit
			Follow-up Lens 1 §	Dispense Lens 2			
[REDACTED]	[REDACTED]	[REDACTED]	[REDACTED]	[REDACTED]	[REDACTED]	[REDACTED]	[REDACTED]
[REDACTED]	[REDACTED]	[REDACTED]	[REDACTED]	[REDACTED]	[REDACTED]	[REDACTED]	[REDACTED]
[REDACTED]	[REDACTED]	[REDACTED]	[REDACTED]	[REDACTED]	[REDACTED]	[REDACTED]	[REDACTED]
[REDACTED]	[REDACTED]	[REDACTED]	[REDACTED]	[REDACTED]	[REDACTED]	[REDACTED]	[REDACTED]
[REDACTED]	[REDACTED]	[REDACTED]	[REDACTED]	[REDACTED]	[REDACTED]	[REDACTED]	[REDACTED]
[REDACTED]	[REDACTED]	[REDACTED]	[REDACTED]	[REDACTED]	[REDACTED]	[REDACTED]	[REDACTED]
[REDACTED]	[REDACTED]	[REDACTED]	[REDACTED]	[REDACTED]	[REDACTED]	[REDACTED]	[REDACTED]
[REDACTED]	[REDACTED]	[REDACTED]	[REDACTED]	[REDACTED]	[REDACTED]	[REDACTED]	[REDACTED]
AEs	X	X	X	X	X	X	X
Device deficiencies	X	X	X	X	X	X	X
Exit Form	(X)	(X)	(X)	(X)	(X)	X	(X)

\* Source only

§ Subjects are required to wear the study lenses for a minimum of 6 hours on the day of follow-up visits prior to the visit.

[REDACTED]

Printed By:

Print Date:

## 1.1 Abbreviations

Abbreviation	Definition
ADE	Adverse device effect
AE	Adverse event
ASADE	Anticipated serious adverse device effect
BCVA	Best corrected visual acuity
Biofinity	CooperVision Biofinity contact lenses
CDMA PL	Clinical development and medical affairs project lead
CFR	Code of Federal Regulations
D	Diopter(s)
D/C	Discontinue
eCRF	Electronic case report form
EDC	Electronic data capture
FDA	US Food and Drug Administration
GCP	Good Clinical Practice
ICF	Informed consent form
IEC	International ethics committee
IP	Investigational product
IRB	Institutional review board
ISO	International Organization for Standardization
LID	Lens identification
LogMAR	Logarithm of the minimum angle of resolution
mm	Millimeter
MOP	Manual of procedures
MR	Manifest refraction
N/A	Not applicable
OD	Right eye
OS	Left eye
OU	Both eyes
RepleniSH	OPTI-FREE RepleniSH multi-purpose disinfection solution
SAE	Serious adverse event
SADE	Serious adverse device effect
US	United States
USADE	Unanticipated serious adverse device effect
VA	Visual acuity

### 3 INTRODUCTION

#### 3.1 Study Rationale and Purpose

The new contact lens in development is intended for the optical correction of refractive ametropia in persons with non-diseased eyes.

The purpose of this study is to obtain on-eye performance data to inform contact lens product development. The primary endpoint was selected to address the primary objective of the study. Procedures for measurement of these endpoints were selected based on common practice for these assessments. The design of this study is justified based upon preclinical and clinical testing, as described within the Investigator's Brochure. Biofinity contact lenses were chosen as the control product because these lenses have the same wear modality and replacement schedule.

[REDACTED]

#### 3.2 Trial Objective

The primary objective of this study is to describe the clinical performance of an investigational silicone hydrogel contact lens over 30 days of daily wear.

#### 3.3 Risks and Benefits

Contact lenses may offer improved peripheral vision and the convenience of not wearing spectacles. Material properties and design characteristics of the contact lens in development are features consistent with successful contact lens wear.

Based upon non-clinical testing and/or documented rationale for applicability of test results to the IP, the new contact lens in development is assessed to be non-toxic and biocompatible for on-eye use.

Biofinity contact lenses are commercially available for daily wear use under a monthly wear modality; further details on any known potential risks and benefits can be found in the package insert.

A summary of the known potential risks and benefits associated with the new contact lens in development can be found in the Investigator's Brochure. Risks are minimized by

compliance with the eligibility criteria and study procedures, and through close supervision by a licensed clinician during exposure to the study lenses. The potential harms associated with on-eye exposure to the new lens materials include toxicity response, blurred vision and ocular discomfort. In general, the risks with the new contact lens in development are anticipated to be similar to other marketed weekly/monthly soft contact lenses.

The site personnel will educate subjects on proper hygiene and lens handling, and compliance with the use of contact lenses according to the protocol. Subjects should be instructed not to wear contact lenses while sleeping or swimming. The site personnel will also advise the subjects to remove contact lenses and return for prompt follow-up of symptoms, such as ocular discomfort, foreign body sensation, excessive tearing, vision changes, or hyperemia.

### **3.4 Subject Population**

The study population includes approximately 36 volunteer subjects to be enrolled at approximately 3 sites, with approximately 12 subjects enrolled per site.

To account for potential screening failure and early discontinuation, approximately 36 subjects are expected to be enrolled to obtain a target of 32 completed subjects.

Subjects must be screened according to the full list of inclusion/exclusion criteria in Section 1 of this protocol. The study population will consist of subjects with normal eyes who are adapted, existing wearers of weekly/monthly soft contact lenses in both eyes, and require contact lens sphere power from -1.00 to -6.00 D.

Rescreening of subjects is allowed only for the following criteria and under the following conditions:

- INC01 – subject must be at least 18 years of age
- EXC13 – participation in a clinical trial within the previous 7 days or currently enrolled in another clinical trial
- A protocol amendment potentially changes eligibility of previously screened and excluded subjects

A subject may only be rescreened once and rescreening should take place within one week of the original screening date.

### 3.5 Outline of Study

This will be a multi-site, prospective, randomized, subject-masked study comparing 2 contact lenses. The duration of subject participation in the study is up to 64 days, with 5 scheduled visits. The study is expected to be completed in approximately 3 months.

## 4 TREATMENTS ADMINISTERED

Subjects will be randomized in a 1:1 manner to receive treatment in crossover sequence: Test product then Control product or Control product then Test product, respectively.

### 4.1 Identity of Study Treatments

DESCRIPTION OF TEST AND CONTROL PRODUCTS		
	Test Product	Control Product
LID Number	LID017569	N/A
Lens identified in randomization system as:	LID017569	Biofinity
Material	██████████	comfilcon A
Water Content	55% (Target)	48%
Base Curve (mm)	8.4 (Target)	8.6
Diameter (mm)	14.2 (Target)	14.0
Rx powers to be available in this study (D)	-1.00 to -6.00 (0.25 steps)	-1.00 to -6.00 (0.25 steps)
Packaging, Labeling, and Supply	
 
• Blister foil pack
 
• Foil label includes at a minimum: 
 
- identifier
 
- base curve
 
- diameter
 
- manufacturing protocol number
 
- packing solution
 
- power
 
- lot number
 
- expiration date
 
- content statement
 
- investigational device statement
 
 
 
	
 
• Blister foil pack
 
• Commercial foil
 
• Available in commercial boxes of ~6 lenses per box
 
• Lenses should be stored at room temperature.
 

	
 
- Sponsor information
 
- country of origin
 
• Provided in packages of approximately 20 lenses per power identified with the following at a minimum:             
 
- color coded label stating the protocol number
 
- material identifier
 
- power
 
- an investigational use only statement
 
- tracking number
 
 
 
• Lenses should be stored at room temperature.
 
	
Usage	
 
• Wear:             
 
○ Daily Wear
 
○ Bilateral
 
○ Crossover according to randomization
 
 
 
• Replacement period: Replacement lenses will not be provided to the subject. In the event a lens needs to be replaced, the subject must return to the site for a replacement lens. Until the replacement lens is obtained, the subject must store the fellow lens in the provided lens care solution and wear their habitual spectacles.
 
• Exposure: At least 8 hours per day, 5 days per week, over a 30-day period (per study lens).
 
• Lens Care: Cleaned and disinfected with RepleniSH
 
	
Control lens procurement	Each site will procure their own control lenses. Refer to the study specific MOP for detailed instructions.	

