## 5.2 Unscheduled Visits

Any visit that occurs between regularly scheduled visits is an Unscheduled Visit. If a subject requires an Unscheduled Visit, he/she must be advised to return to the office wearing the study lenses, if at all possible (unless he/she is experiencing a sign or symptom [as indicated in Section 3.3 Risks and Benefits]). During all unscheduled visits, the Investigator must conduct the following procedures:

- Collect AE and Device Deficiency information
- Assess and record changes in medical condition or concomitant medication
- Assess and record VAs
- Perform biomicroscopy (assessments with or without lenses, as possible)

In addition, all procedures for Visit 5 (Follow-up/Exit) should be completed (as possible). The Investigator may perform additional procedures for proper diagnosis and treatment of the subject. The Investigator must document this information in the subject's case history source documents.

If during an Unscheduled Visit the subject is discontinuing the study lenses or discontinuing from the study, the Investigator must conduct Exit procedures according to Table 1-1: Schedule of Study Procedures and Assessments, as possible.

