### 6.1 Subject Evaluability

The final subject evaluability will be determined prior to breaking the code for masked treatment (lens) sequence assignment and locking the database, based on the Deviations and Evaluability Plan.

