## 4 Effectiveness Analysis Strategy

This study defines one primary endpoint [REDACTED]. The safety analysis set will be used for all effectiveness analyses.

Continuous variables will be summarized using the number of observations, mean, standard deviation, median, minimum, and maximum. Categorical variables will be summarized with counts and percentages from each category.

All data obtained in evaluable subjects/eyes will be included in the analysis. No imputation for missing values will be carried out.

A listing of selected effectiveness data will also be provided.

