## 4.3 Statistical Methods for Effectiveness Analyses

### 4.3.1 Primary Effectiveness Analyses

Descriptive statistics (number of observations, mean, standard deviation, median, minimum, maximum) for the logMAR values will be presented.

[Redacted]

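### Do mid-period lens replacements and unscheduled acuity readings leave the primary acuity summary undefined?

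*Protocol*

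**What the plan says.** On replacement, Protocol 4.1 (Usage) states: "In the event a lens needs to be replaced, the subject must return to the site for a replacement lens". Until then the fellow lens is stored and the subject wears spectacles. The exposure line in the same table reads "At least 8 hours per day, 5 days per week, over a 30-day period (per study lens"). No limit is put on the day of replacement, and no passage restarts the visit schedule.

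On timing, Protocol Table 1-1 and SAP Table 1-1 count each product from its own Day 1 and place Month 1 at Day 30 ± 2. Protocol 3.5 adds: "The duration of subject participation in the study is up to 64 days, with 5 scheduled visits".

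On unscheduled visits, Protocol 5.2 says of the subject that "he/she must be advised to return to the office wearing the study lenses, if at all possible", and then makes an exception for anyone with a sign or symptom of the kind described in Section 3.3. Its list of mandatory procedures includes "Assess and record VAs", without naming the correction. Table 1-1 gives acuity with study lenses only a bracketed, conditional mark in the unscheduled column.

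On analysis, SAP 4.3.1 states: "Descriptive statistics (number of observations, mean, standard deviation, median, minimum, maximum) for the logMAR values will be presented". SAP 4 adds: "All data obtained in evaluable subjects/eyes will be included in the analysis", followed by the rule against imputation. Protocol 6.1 settles evaluability before the code is broken, "based on the Deviations and Evaluability Plan". That plan is not among the documents, and text after SAP 4.1 and 4.3.1 is redacted.

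**The concern.** The objective is to describe performance across 30 days of wear, and the Month 1 acuity row is where a reader looks for it. If some eyes in that row are in lenses dispensed one, two or three weeks late, the row mixes lens ages and nothing visible says how many.

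The unscheduled visit raises a second question. A subject returning for a replacement may have acuity measured, and that reading could be a poor one. Read literally, the all-data sentence in SAP 4 would include it; a table of scheduled visits would leave it out. Early exit raises the same question, because Protocol 5.3 has the Visit 5 procedures done then, whichever lens is being worn.

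Because no hypothesis is tested, the descriptive table is the result. Two programmers working from the visible text could in principle report a different n, standard deviation and maximum for the primary endpoint.

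**Working it through.** **1. The plan's own figure.** The latest Month 1 day is 30 + 2 = 32. Two periods give 2 × 32 = 64 days, which matches Protocol 3.5. (Counting the shared Visit 3 day once gives 63.) The stated duration therefore leaves no room to restart a period after a replacement.

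**2. Age of a replaced lens at Month 1.** With dispensing as Day 1, a lens replaced on Day d and seen on Day v is on its own Day v − d + 1, where v runs from 28 to 32.

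| Replaced on | Own day at v = 28 / 30 / 32 |
|---|---|
| Day 3 | 26 / 28 / 30 |
| Day 5 | 24 / 26 / 28 |
| Day 6 | 23 / 25 / 27 |
| Day 8 | 21 / 23 / 25 |
| Day 15 | 14 / 16 / 18 |
| Day 22 | 7 / 9 / 11 |

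Day 5 is the last replacement day that can give 28, and only at the latest permitted visit. At the nominal Day 30 visit it is Day 3. In elapsed days the limit is Day 4. The 28-day mark used here is the lower edge of the visit window (30 − 2). It is not a lens-age requirement in either document.

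**3. Effect of replaced lenses on the Month 1 mean.** 32 completers × 2 eyes = 64 eyes per product, so one eye is 1/64 = 1.6%. The shift is k × δ / 64. The documents give no replacement rate and no acuity difference, so both are assumed: 5–20% of eyes (k = 3 to 13) and δ = 0.02 to 0.10 logMAR, in either direction.
- Low: 3 × 0.02 / 64 = 0.001
- High: 13 × 0.10 / 64 = 0.020

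**4. Effect of one unscheduled reading x added to a row of n eyes** with mean 0 and standard deviation s (all assumed). The mean shift is x/(n + 1). The new SD is √{[(n − 1)s² + x²·n/(n + 1)]/n}.
- n = 64, s = 0.08, x = 0.30: mean +0.30/65 = 0.005; SD = √{[63 × 0.0064 + 0.09 × 64/65]/64} = 0.088, up from 0.080.
- n = 64, s = 0.10, x = 0.20: SD 0.102 (+2%).
- n = 64, s = 0.06, x = 0.40: SD 0.0775 (+29%).
- Pooled over dispensing, Week 1 and Month 1, n = 3 × 64 = 192; with s = 0.08 and x = 0.30, mean +0.30/193 = 0.002 and SD 0.083 (+3%).

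The maximum would become 0.30. For 64 independent normal readings the expected maximum is about 2.34 SD (simulated), or 2.34 × 0.08 = 0.19. The maximum is the statistic that would visibly move.

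**5. Would that reading exist, and would it land in the row?** Protocol 3.3 has subjects with vision changes take their lenses out and come back promptly, and the exception in 5.2 covers those subjects. A subject whose lens is lost or torn is in spectacles under 4.1. Study-lens acuity at an unscheduled visit is conditional in Table 1-1. For the reading to enter a 64-eye Month 1 row, someone would also have to assign unscheduled visits to scheduled ones, and no visible rule does that.

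**The case for a change.** The strongest opposing argument is that the SAP is more explicit about secondary matters than about its primary endpoint. SAP 5.3.2 tabulates biomicroscopy by visit and says which visits its listings cover, and SAP 5.3.1 assigns each adverse event to a lens by onset. For acuity the visible text names six statistics and no visit. The protocol plainly expects replacements: Table 1-1 allows dispensing at an unscheduled visit, and torn or defective lenses are named as device deficiencies in Section 7.1. A short sentence fixed before unmasking would remove a data-dependent choice at almost no cost.

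Part of this stands. The visible SAP does not state the convention, and Protocol 5.2 and Table 1-1 are not aligned on whether study-lens acuity is required at unscheduled visits; those passages should be reconciled as a matter of tidiness.

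The rest does not amount to a defect. The documents use Lens 1 and Lens 2 for the two products, so the exposure line reads naturally as per product. A replacement lens of the same product therefore continues the planned exposure. The all-data sentence sits under missing data in Protocol 6.6, next to the no-imputation rule, and is poor evidence of an instruction to pool unscheduled readings. An early-exit reading on Lens 1 does not fit the Visit 5 column, which Table 1-1 defines as Lens 2, Day 30 ± 2. Torn and defective lenses will already be visible through the device-deficiency table and listing, and SAP 4 plans a listing of effectiveness data.

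**Conclusion.** The calendar point is correct, but it does not call for a change. A replaced lens will be younger than 28 days at Month 1 if replaced after Day 5, yet no requirement is breached and the reading remains valid for its product. What is left is an unstated tabulation convention that analysts would fill sensibly: acuity by product and scheduled visit, with anything unscheduled kept to listings. Writing that down, or counting eyes in replacement lenses at Month 1, would be optional extra reporting.

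The likely effect is small: at most about 0.020 logMAR on the Month 1 mean over the assumed range for replaced lenses, and 0.003 to 0.006 from one stray reading of 0.20 to 0.40 in a 64-eye row. The SD and maximum could move more, but only if an unscheduled on-lens reading existed and were placed in that row. These figures rest on assumed replacement rates, acuity differences and SDs, and on 64 completer eyes, whereas the analysis set is all exposed eyes. The direction is unknown, and SAP 4.2 and the SAP executive summary confirm that no hypothesis or success decision depends on the result. The redacted text and the Deviations and Evaluability Plan could settle the convention either way; the conclusion does not depend on what they say.
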